9.6.2 Pregnancies

The investigator must report to the sponsor any pregnancy occurring in a female study patient during her participation in this study. The outcome of the pregnancy should be followed up carefully, and any outcome of the mother and the child at delivery should be reported.

The child’s health should be followed up until up to 4 weeks after discharge.

For a pregnancy in the partner of a male study patient, all efforts will be made to obtain similar information on course and outcome, patient to the partner’s consent.

For all reports, the forms provided are to be used. The investigator should submit them within the same timelines as an SAE.

9.6.3 Further safety

Safety assessments will include adverse events (AEs), physical examination findings, and vital signs including pulse rate and blood pressure assessment. Laboratory safety studies will include blood chemistry, hematology, and urine pregnancy testing (performed in women of childbearing potential) (see Section [9.7](#)).

Adverse events may occur during clinical trials from overdose (whether accidental or intentional), from abuse and from withdrawal. In this trial, any dose higher than the maximal target dose prescribed in the study protocol will be considered an overdose. If an adverse event(s) is resulted from the overdose, the adverse event(s) is reported as a non-serious adverse event, unless other serious criteria are met.

In the event of an overdose, the investigator/treating physician should contact the Medical Monitor immediately and closely monitor the participant for any AE/SAE and laboratory abnormalities for at least 4 days. Sponsor does not recommend specific treatment for an overdose.

Medical devices:

The following is Japan specific guidance for reporting medical device failures:

The investigator must report immediately all non-approved medical device failures which could cause health damage, as well as any health damage that may be causally associated with a non-approved medical device failure. For this reporting, the forms provided are to be used and sent to the designated recipient.

9.7 Other procedures and variables

9.7.1 Laboratory assessments

9.7.1.1 Local laboratory

At the screening visit, local laboratory results from routine clinical examinations will be assessed to check the eligibility of the patient.

At least the following parameters must be measured at the screening visit and entered in the eCRF to check the patient's eligibility for the study:

- NT-proBNP or BNP for screening (see Section [9.7.7](#) for further details)
- Serum creatinine for screening (eGFR will be calculated automatically in the eCRF using the MDRD formula)
- urine pregnancy test, and Serum β -human chorionic gonadotropin (unless requested by local authorities, serum β -human chorionic gonadotropin will only be conducted if urine pregnancy test is positive)

Urine or serum pregnancy test will also be conducted on visits 2 and 7 for women of childbearing potential, according to the local regulations. If required by national / institutional regulations, a serum or urine pregnancy test in patients of childbearing potential should be performed more often (e.g. at every visit).

9.7.1.2 Central Laboratory

Only centrally analyzed blood samples will be considered for analysis.

The name and address for the central lab service provider can be found in the documentation supplied by the vendor. The following laboratory tests will be performed centrally:

Hematology: Hct, Hb, MCV, MCH, MCHC, Platelet count, RBC, RDW, Reticulocytes, and WBC.

Chemistry: ALT, AST, LDH, Bilirubin (Total), Blood glucose, cholesterol (HDL, LDL, total), triglycerides, BUN, creatinine, GGT, K, Na, and Uric acid, high-sensitivity troponin t, HbA1c.

Biomarker: NT-proBNP.

Coagulation: aPTT, INR

In the event of implausible results, the laboratory may measure additional parameters to assess the quality of the sample (e.g. clotted or hemolyzed) and to verify the results. The results from such additional analyses may neither be included in the clinical database of this study nor evaluated further. If the results are relevant, the investigator will be informed to determine follow-up activities outside of this protocol.

9.7.2 Physical examination

Full physical examination should be performed by the investigator at Screening and randomization. Physical exams focused on CV assessment will be performed at the other visits. Abnormal physical examination findings are recorded either as medical history or as adverse events (see Section 9.6.1.1).

9.7.3 Echocardiography parameters

Echocardiography data from routine clinical exam will be assessed at screening to determine eligibility, according to the following criteria:

- LVEF $\geq 45\%$ and
- Structural changes indicated by at least one of the following parameters:
 - LV hypertrophy (any of the following: intraventricular septal or posterior wall thickness ≥ 1.1 cm) and/or LV mass index ≥ 115 g/m² in male and ≥ 95 g/m² in female)
 - LA enlargement (any of the following: LAV index ≥ 29 ml/m², or LAV >58 mL in male and >52 mL in female patients, or LA area >20 cm², or LA diameter >40 mm in male and >38 mm in female patients)

9.7.4 12-lead ECG

ECGs will be transferred and analyzed centrally. The reading will be done in a standard way. Standard electrocardiogram (12-lead ECG) in supine position will be recorded after resting for at least 10 min as follows:

1. ECG at baseline in all patients to evaluate the eligibility of the patient for PK/QT assessment. The eligibility for PK/QT will be defined by the investigator in the baseline ECG.

The ECG is **invalid** for QT assessment if at least one of the following is fulfilled:

- QRS-Prolongation >120 ms, e.g. in the presence of complete bundle branch block
- Pacemaker stimulation
- Arrhythmia and conduction abnormalities such as atrial fibrillation or flutter, 2nd - 3rd degree AV block with ventricular escape rhythm etc.
- Marked sinus arrhythmia

2. ECG matched with PK

The ECG will only be performed for patients who are eligible for PK/QT assessment. It will be recorded at visits 2, 5 and 9 just before collection of the blood sample for PK analysis. Non-concordance with subsequent assignment as evaluable or non-evaluable upon central processing by the ECG core lab using different methods for QT assessment will be descriptively summarized and not be considered as deviation.

3. ECG at the end of treatment and in case of premature discontinuation as a safety measure in all patients (for patients who are eligible for PK/QT, assessment as part of PK/QT collection).

Only the results of the central evaluation will be used for statistical evaluation of ECG data. The following ECG parameters will be analyzed: HR, PR, QRS duration (QRSD), QT, and QTc (QTcB and QTcF).

The ECGs must be recorded with a paper velocity of 25 mm per second. The ECG print-outs will be identified with the PID as well as date and time of recording and will be attached to the patient's file.

All ECGs will be examined by the investigator, and any new clinically relevant abnormality will be documented as an AE.

9.7.5 Vital signs

BP and pulse rate measurements will be performed at specific visits. For details see Section [9.2](#).

Accurate measurement of blood pressure is essential to guide dose titration management and to detect potential safety signals during the trial. A number of factors related to the patient can cause significant deviations in measured blood pressure. These include room temperature, exercise, alcohol or nicotine consumption, positioning of the arm, muscle tension, bladder distension, talking, and background noise.

Blood pressure and pulse rate should be measured under the following conditions:

- Measurement of pulse rate and blood pressure must be conducted after 10 minute resting period with patient comfortably seated in a chair with the legs uncrossed and the back and arm supported. Measurements should not be made while the patient is on an examining table. The patient should be instructed to relax as much as possible and to not talk during the measurement procedure
- The examiner should ensure that the middle of the cuff on the upper arm is at the level of the right atrium (the mid-point of the sternum).
- The patient should be asked to remove all clothing that covers the location of cuff placement.
- The same examiner should assess the patient at all subsequent visits and use the same device under same external conditions.
- The protocol requires 3 measurements – approximately 2 min apart (means will be calculated in the eCRF). Please record the time, positioning and arm used for each measurement

9.7.6 Biomarkers

NT-proBNP will be determined at the time points indicated in Section [9.1](#). Details on the collection, processing, storage and shipment of biomarker samples will be provided in separate documents (e.g. sample handling sheets or lab manual)

Other biomarkers deemed relevant to gain further knowledge about the mechanisms of the disease or about the drug (i.e. mode of action related effect or safety of the drug) may be measured, based on newly emerging data from other ongoing studies and / or literature data but only in countries where it is not excluded by local guidelines.

The additional biomarker results may be reported separately.

9.7.7 Optional pharmacogenetic research

Understanding genetic determinants of drug response is an important endeavor during medical research. This research will evaluate whether genetic variation within the studied clinical trial population correlates with baseline clinical characteristics and the course of disease for the studied outcomes and/or ii) response to the study drug treatment. If genetic variation is found to correlate with clinical characteristics and outcomes, the data might point to novel pathways involved in the disease and thereby inform development of novel medicines. If genetic variation is found to predict efficacy or adverse events, the data might inform optimal use of therapies in the patient population. This research contributes to understanding genetic determinants of the disease in general, as well as efficacy and safety associated with the treatments in this study.

A whole blood sample will be obtained from those patients, who have signed a separate informed consent form for pharmacogenetic research, but only in countries where it is not excluded by local guidelines. The participation in this part of the study is voluntary and has no influence on the participation in this study.

Results will be reported under separate cover, if the evaluations are performed.

9.7.8 Accelerometry

At sites participating in the accelerometry substudy, it is planned that up to approximately 150 patients may consent to undergo activity tracking before randomization, before visit 7, and before visit 9 (end of treatment at 24 weeks).

Subjects are not required to participate in the accelerometry substudy in order to participate in the main trial. In addition, subjects must provide separate informed consent in order to participate in this substudy.

Additional details will be specified in separate site accelerometry procedure manuals and accelerometry substudy analysis plans.

9.8 Appropriateness of procedures / measurements

All parameters, as well as the methods to measure them, are standard variables / methods in clinical studies and / or clinical practice. They are widely used and generally recognized as reliable, accurate, and relevant.

10. Statistical methods and determination of sample size

10.1 General considerations

Statistical analysis will be performed using Statistical Analysis Software; the version used will be specified in the statistical analysis plan.

10.2 Analysis sets

FAS: All subjects randomized and treated (at least one dose of the study treatment), and have at least one observed outcome measure, will be valid for the FAS. The patients will be analyzed based on the planned treatment. The primary analysis for all efficacy endpoints will be based on FAS.

SAF: All patients that received at least one dose of study treatment (vericiguat or placebo). Analyses will be based on actual treatment received, and patients who did not reach maximum titration or received both vericiguat and placebo by mistake will be assigned to the planned treatment. All safety analyses will be based on the SAF.

PPS: All patients who meet the major inclusion and exclusion criteria at randomization that may affect efficacy, who are not taking excluded concomitant medications during the study that could have an effect on efficacy, have the KCCQ assessed at baseline and at least once during the main treatment phase and who are at least 80% compliant with study medication and show no major protocol deviations. The detailed criteria will be described in the SAP. The PPS will only be used in the supportive analysis.

PKS: All subjects with at least one valid pharmacokinetic concentration will be included in the statistical evaluation of pharmacokinetics.

10.3 Variables and planned statistical analyses

10.3.1 Efficacy variables

Primary efficacy variable: The primary endpoint will be change in KCCQ PLS from baseline to week 24.

The estimand of interest is the de facto or treatment policy estimand.

Population: Defined through appropriate inclusion/exclusion criteria (see Section 6.1 and 6.2) to reflect the targeted patient population.

Variable: Change from baseline in KCCQ PLS from baseline to Week 24.

Measurement of intervention effect: Regardless of stopping study treatment or adherence to study treatment.

Summary measure: Difference of LS means at Week 24.

The analysis will include all assessments post-baseline. Graphical method of Maurer and Bretz (33) will be applied for multiplicity control. The two primary hypotheses will be tested with an equally splitted two sided alpha level of 0.025.

The primary analysis of the primary endpoint will be performed using a MMRM, including treatment group (vericiguat versus placebo), study visit as fixed effects, patient as a random effect, interaction between study visit and treatment group, and adjustment for the baseline PLS values as covariates. The model will assume an unstructured covariance matrix for within-patient variability.

The analysis will be performed in the Full Analysis Set. For patients who drop out of the study, a pattern-mixture model with control-based pattern imputation will be implemented. After the patient drops out from the study, it is assumed that patients from the vericiguat arm

will show the same future trend as those on the placebo arm. Patients that discontinue from the placebo arm are assumed to evolve in the same way as placebo patients that remain in the study. For those patients who had died during the study, they will be imputed with the worst case outcome, i.e., a zero score for missing KCCQ PLS.

The model statement is:

$$Y_{ijklm} = \mu + \beta x_i + t_k + r_l + h_m + v_j + (tv)_{jk} + s_i + \varepsilon_{ij}$$

where Y_{ijklm} is the change from baseline in PLS to visit j for patient i; μ is the intercept, β is the baseline covariate effect, x_i is the baseline PLS for patient i, t_k is the fixed effect of treatment k, r_l is the fixed effect of region l, h_m is the fixed effect of heart rhythm m (atrial fibrillation and sinus rhythm), v_j is the fixed effect of visit j, $(tv)_{jk}$ is the interaction effect of treatment k by visit j, s_i is the random effect of patient i and $\varepsilon_{ij} \sim \text{Normal}(0, \sigma^2)$ represents the residual variance component with $\text{corr}(\varepsilon_{ij}, \varepsilon_{ij'}) = \rho_{jj'}, j \neq j'$

Further, based on the anchor-based interim analysis (see Section 10.5), the percentages of responders with MCID, moderate, and large differences at each visit will be summarized and nominal p-values will also be provided. In addition, cumulative distribution function of change from baseline at 24 weeks for the KCCQ PLS domain will be plotted to compare the proportion of patients who are meeting certain threshold from vericiguat and placebo arms (see Section 10.5).

As a supportive analysis, the MMRM using the above model will be applied to all assessments post-baseline prior to study drug termination.

Additional sensitivity analyses will be performed. Analysis using data imputation approaches based on different missing data mechanisms will be investigated, including tipping point analysis. Details of such methods will be described in the SAP.

Secondary efficacy variable:

The secondary endpoint is change from baseline in the 6 MWT at 24 weeks.

The estimand of interest is the de facto or treatment policy estimand.

Population: Defined through appropriate inclusion/exclusion criteria (see Section 6.1 and Section 6.2) to reflect the targeted patient population and restricted to those who are able to perform the 6 MWT at baseline.

Variable: Change from baseline in 6 MWT from baseline to Week 24.

Measurement of intervention effect: Regardless of stopping study treatment or adherence to study treatment.

Summary measure: Difference of LS means at Week 24.

The secondary endpoint will be analyzed in the same manner as the primary endpoint. For those patients who are too sick to perform the test at any post baseline visit, a score of 0 will be assumed. further sensitivity analyses will be specified in SAP.

Other efficacy variables:

Other continuous variables including change from baseline to week 24 in other KCCQ domains, EQ-5D-5L, fried frailty score and NT-proBNP, will be analyzed using the MMRM

[figure not shown]
model. For categorical variables such as NYHA class, PGIC, PGIS, the relative response level change will be summarized by each visit. Incidences of cardiovascular death and total heart failure hospitalizations, as well as all-cause mortality and CV hospitalizations, MI and stroke will be summarized. Kaplan Meier curves of the composite endpoints (see Section 9.4) will be presented.

Details on any descriptive subgroup analyses will be specified in the SAP. These will include region, gender, atrial fibrillation status, patient randomization time (before or after discharge from HF hospitalization, or post IV diuretic treatment without hospitalization), and the time from HF hospitalization or IV diuretic treatment to randomization (<3 month vs. ≥ 3 month).

Multiplicity adjustment:

The study uses the graphical method of Maurer and Bretz (33) to provide strong multiplicity control across the primary KCCQ PLS hypotheses and the secondary 6 MWT hypotheses. The overall two sided alpha level will be controlled at 0.05. The two primary hypotheses will be tested using Bonferroni procedure, each at a splitted level of alpha 0.025. The two secondary hypotheses will be tested based on parallel gatekeeping principle. If both primary hypotheses can be rejected, the secondary family will be tested at a full alpha level 0.05 (two sided). If only one primary hypothesis is shown to be statistically significant, then only the secondary hypothesis based on the same dose group can be tested at an alpha level carried forward from the primary family testing, i.e., 0.025 (two sided). In this case, if the secondary hypothesis is rejected, the alpha spending associated with this dose group (0.025) will be re-utilized to test the other failed primary hypothesis again. Figure 10-1 shows the α -allocation for each hypothesis in the ellipse representing the hypothesis.

Figure 10-1 α -allocation for each hypothesis in the ellipse representing the hypothesis

Overall, the primary analysis will be claimed to have a positive outcome if the null hypothesis for at least one of the two primary hypotheses can be rejected.

10.4 Determination of sample size

The sample size estimation for this study will be based on the analysis of the primary endpoint of KCCQ PLS at 24 weeks comparing vericiguat 15 mg versus placebo and 10 mg versus placebo, to achieve 80% power with two-sided alpha level of 0.05 to detect a treatment difference from placebo in one or both of the dose groups. A mean difference from placebo in KCCQ PLS of 5 points for both dose groups and a common SD of 21 points are assumed. Under the same assumption of treatment effect and standard deviation, the power to detect

difference for any single comparison will be 65%. The 80% power was based on an “either or” success criterion, i.e., if at least one of the primary null hypotheses is rejected. The marginal power to reject any single comparison is 65%.

The given sample size provides 97% power to detect +30 m placebo-corrected increase in the secondary endpoint 6MWT (assumed SD 80 m) for any one dose group, and 80% power to detect an increase by +22.3 m, which is below the 35 m increase associated with a 6.2 point improvement in KCCQ PLS at 24 weeks in FAIR-HF and greater than the 15 m increase at 3-months that was associated with a 2.3 point improvement in KCCQ PLS in ACTION-HF (34).

A 5 point improvement in KCCQ OSS in patients with HFrEF is considered to represent a clinically significant change in heart failure status (35). Similarly, a change of +6.4 and -5.1 points in KCCQ PLS were associated with either small improvements or small deteriorations in clinical status, as determined by a cardiologist, in the Cardiovascular Outcomes Research Consortium study cohort in patients with HFrEF (35, 36). In addition, baseline KCCQ PLS score has also been associated with peak VO₂ and distance traveled on the 6 minute walk test (6 MWT), with 6.4 and 7.5 point differences in PLS being associated with 1SD changes for peak VO₂ and 6 MWT respectively (37). Furthermore, both anchor-based and distribution-based analyses of the SOCRATES-PRESERVED data support an improvement of 5 points in KCCQ PLS as MCID. This effect size has been proposed to the US FDA during a Type C meeting and was considered preliminarily acceptable pending additional data analyses (see Section 10.5) per Agency correspondence following the meeting. As such, this study will be powered to detect a placebo-corrected change of at least 5 point improvement in KCCQ PLS from baseline to 24 weeks. An SD of 21 points was assumed based on studies in which KCCQ PLS has been reported in the literature (38-43). The patients will also be followed until the end of the study regardless of stopping study treatment or not, hence the drop-out rate is considered negligible. Based on these considerations, the total sample size will be N=735 with N=245 each in the placebo, 10 mg vericiguat arm and 15 mg vericiguat arm in a 1:1:1 randomization.

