10.5 Planned interim analyses

Futility interim analysis

A single interim assessment by the DMC to evaluate futility is planned for when 50% of the patients complete Visit 7 (week 12) and their KCCQ data become available. Although the effects of 24 weeks of treatment with vericiguat have not been evaluated in patients with HFpEF, prior data in this population suggest that the 12 week timepoint will be sufficiently predictive of the 24 week data to allow for an adequate interim assessment of efficacy. Furthermore, in view of the expected timeline for trial conduct, a sufficiently large proportion of data at the 24 week timepoint will only become available shortly before completion of the trial. Based on a careful analysis of the operating characteristics of a range of futility criteria, an observed treatment effect of 0.6 point difference in KCCQ PLS (vericiguat vs placebo) was chosen to serve as the boundary for futility for both dose groups; this is approximately equivalent to a joint conditional power (CP) of 23% (under the assumption of a true difference of 5 points). An observed treatment effect <0.6 in both comparisons would therefore signal to the DMC to consider their potential recommendation that the trial should be terminated early. The type II error rate spent with this futility rule will be <0.01. Assuming the true treatment

effect is a 5 point difference as expected, the probability of stopping at the interim is approximately 1.3%. Under the null hypothesis, i.e., assuming 0 treatment effect for both vericiguat vs. placebo comparisons, the probability of stopping at the interim for futility for both doses is approximately 43%. Stopping for futility will only be done if both arms are futile. If only one arm is futile then it will not be dropped as enrollment is expected to be completed at the time of the futility analysis. At this futility boundary the trial has a probability of 9% to observe a >5 point improvement in either of the comparison in KCCQ PLS. Details of the futility analysis will be specified in the SAP and in the DMC charter. No formal interim report will be written.

Anchor-based interim analysis

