## **2. Study Objectives**

The primary hypothesis is treatment with vericiguat 10 mg or 15 mg in patients with HFpEF improves physical functioning measured by the KCCQ PLS compared to placebo after 24 weeks of treatment. The secondary hypothesis is treatment with vericiguat 10 mg or 15 mg in patients with HFpEF improves walking distance as measured by the 6MWT compared to placebo after 24 weeks of treatment. The study is designed to have enough power for the primary and secondary hypotheses testing. Other objectives are listed only for descriptive purposes.

Primary objectives:

- To evaluate the efficacy of vericiguat 10 mg in comparison to placebo on improving physical functioning as measured by KCCQ PLS from baseline to week 24.
- To evaluate the efficacy of vericiguat 15 mg in comparison to placebo on improving physical functioning as measured by KCCQ PLS from baseline to week 24.
- To evaluate the safety and tolerability of vericiguat.

Secondary objectives:

- To evaluate the efficacy of vericiguat 10 mg in comparison to placebo on improving distance traveled on a 6MWT from baseline to week 24.
- To evaluate the efficacy of vericiguat 15 mg in comparison to placebo on improving distance traveled on a 6MWT from baseline to week 24.
- To evaluate the efficacy of vericiguat 10 mg in comparison to placebo in increasing the proportion of patients with KCCQ PLS improvement from baseline by >5 points at 24 weeks and other thresholds (e.g. >3, >7, >10, >15, >20), and the proportions with these improvements in the other KCCQ domains OSS, CSS, TSS and SFS.

- To evaluate the efficacy of vericiguat 15 mg in comparison to placebo in increasing the proportion of patients with KCCQ PLS improvement from baseline by >5 points at 24 weeks and other thresholds (e.g. >3, >7, >10, >15, >20), and the proportions with these improvements in the other KCCQ domains OSS, CSS, TSS and SFS.
- To evaluate the efficacy of vericiguat 10 mg in comparison to placebo in decreasing the proportion of patients with KCCQ PLS decline from baseline by >5 points at 24 weeks and the proportions with decline in the other KCCQ domains OSS, CSS, TSS and SFS.
- To evaluate the efficacy of vericiguat 15 mg in comparison to placebo in decreasing the proportion of patients with KCCQ PLS decline from baseline by >5 points at 24 weeks and the proportions with decline in the other KCCQ domains OSS, CSS, TSS and SFS.

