### 6.2.5 Multiplicity adjustment

The study uses the graphical method of Maurer and Bretz [22] to provide strong multiplicity control across the primary KCCQ PLS hypotheses and the secondary 6 MWT hypotheses. The overall two-sided alpha level will be controlled at 0.05. The two primary hypotheses will be tested using the Bonferroni procedure, each at a splitted level of alpha 0.025. The two secondary hypotheses will be tested based on a parallel gatekeeping principle. As shown in Figure 6-1, if the test of both primary and secondary endpoints at one of the dose groups is significant at the alpha level of 0.025, the primary and secondary endpoint at the other dose group can be tested at the alpha level of 0.05, in an ordered manner. Figure 6-1 shows the  $\alpha$ -allocation for each hypothesis in the circle representing the hypothesis.

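### Protocol 10.4 gives 6MWT powers of 97% and 80% without saying they ignore the gatekeeping; under its own 5-point PLS assumption, per-dose power is at most about 71%

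*Protocol*

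**What the plan says.** Protocol 10.4 bases the sample size on the primary endpoint: 245 patients per arm, a 5-point PLS difference from placebo in both doses, SD 21. It distinguishes 80% power to succeed on at least one dose from the power of one comparison: "The marginal power to reject any single comparison is 65" per cent.

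The next paragraph turns to the secondary endpoint. It says that the planned N "provides 97% power to detect +30 m placebo-corrected increase in the secondary endpoint 6MWT (assumed SD 80 m) for any one dose group". For the smaller effect the wording is: "and 80% power to detect an increase by +22.3 m". No alpha is attached to either figure, and nothing says whether the gatekeeping is counted.

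The gatekeeping is in Protocol 10.3.1. Each primary hypothesis is tested at 0.025. If only one is rejected, "then only the secondary hypothesis based on the same dose group can be tested", also at 0.025. If that 6MWT test succeeds, its alpha "will be re-utilized to test the other failed primary hypothesis again". If both primaries are rejected, the 6MWT family is tested at 0.05. SAP 6.2.5 describes the same graph: once both endpoints of one dose are significant at 0.025, "the primary and secondary endpoint at the other dose group can be tested at the alpha level of 0.05, in an ordered manner".

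**The concern.** A 6MWT claim for a dose requires two rejections: that dose's PLS hypothesis, then its 6MWT hypothesis. Protocol 10.4 puts the first step at 65% per dose, yet the next paragraph gives 97% or 80% for the second endpoint with no qualification. A reader who takes those figures as the chance of a formal 6MWT success for a dose would be well above what the plan offers under its own assumptions.

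The 6MWT is the only secondary endpoint inside the strong multiplicity control, so its chance of formal success is a design property that readers of 10.4 will want. What is at stake is the accuracy of a stated power; the validity of the tests is not affected.

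**Working it through.** **Inputs.** From Protocol 10.4: 245 per arm, negligible drop-out, PLS effect 5 points in both doses with SD 21, 6MWT effects 30 m and 22.3 m with SD 80 m. From Protocol 10.3.1 and SAP 6.2.5: two-sided 0.025 per dose (critical value 2.241), rising to 0.05 (critical value 1.960) after recycling. The documents give no correlation between PLS and 6MWT, so it is varied from 0 to 1. All calculations use the normal approximation.

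**Step 1: reproduce the stated 6MWT powers.** The standard error of a difference is 80 × √(2/245) = 7.228 m. Power = Φ(effect/SE − critical value).

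| 6MWT effect | Effect/SE | Power at 0.025 | Power at 0.05 | Stated |
|---|---|---|---|---|
| 30 m | 4.150 | Φ(1.909) = 97.2% | 98.6% | 97% |
| 22.3 m | 3.085 | Φ(0.844) = 80.1% | 87.0% | 80% |

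The stated figures match at 0.025 and not at 0.05. They are single-comparison powers that take the split alpha but leave out the precondition on PLS.

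**Step 2: reproduce the primary powers.** SE = 21 × √(2/245) = 1.897 points, and 5/1.897 = 2.635. Per-dose power at 0.025 = Φ(2.635 − 2.241) = 65.3%. The two PLS statistics share the placebo arm, so their correlation is 0.5. The bivariate normal then gives P(both exceed 2.241) = 50.0%, and P(at least one) = 65.3% + 65.3% − 50.0% = 80.6%. Both match the stated 65% and 80%.

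**Step 3: ceiling on per-dose 6MWT power.** Suppose every 6MWT test succeeds when it is allowed. Dose b's 6MWT can then be rejected if its PLS passes at 0.025, or if it passes only at 0.05 while dose a's PLS passes at 0.025, since recycling then lifts dose b to 0.05:

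P(Zb > 2.241) + P(1.960 < Zb ≤ 2.241, Za > 2.241) = 0.6531 + 0.0543 = 0.7074.

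The ceiling is 70.7% per dose. It needs no assumption about the 6MWT effect or its correlation with PLS. Testing the 6MWT family at 0.05 when both primaries succeed does not raise it, because 6MWT power is already set to 100% here.

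**Step 4: power at 30 m in both doses.** The SAP 6.2.5 graph was simulated with 2,000,000 trials per correlation (Monte Carlo SE about 0.0003).

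| PLS/6MWT correlation | Per dose | At least one dose |
|---|---|---|
| 0 | 69.3% | 79.5% |
| 0.3 | 69.9% | 79.9% |
| 0.5 | 70.3% | 80.2% |
| 0.7 | 70.6% | 80.5% |
| 1.0 | 70.7% | 80.6% |

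**Step 5: dependence on the PLS effect.** Repeating step 3 with other true PLS effects gives a ceiling of about 74% at 5.2 points and 89% at 6.2 points.

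**Not included.** Protocol 10.5 says that under a 5-point effect "the probability of stopping at the interim is approximately 1.3" per cent. The futility look could therefore lower these figures by at most about 1.3 percentage points.

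**The case against.** The best defence is that no stated figure is miscalculated. Protocol 10.4 says the sample size rests on the primary endpoint; the 6MWT sentence only reports what that size provides for one comparison. The 65% stands just before it and the gatekeeping is in the preceding section, so a careful reader can infer that 97% is not the chance of a formal success. Quoting stand-alone power for a secondary endpoint is not in itself an error. All of that stands, and it is why the point is minor.

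It does not remove the point. The alpha needed to reproduce the figures is missing: the two-sided level named in 10.4 is 0.05, which gives 98.6% and 87.0%. The same section labels the PLS figures as either-or or marginal and leaves the 6MWT figures unlabelled. Reading the phrase about one dose group as at least one dose does not rescue 97% either, since the cap is then the 80.6% either-or primary power.

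The defence is also right that the ceiling depends on the assumed PLS effect, as step 5 shows. It has to be stated with that condition.

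**Conclusion.** The point holds as a minor one. Under the protocol's planning case (true 5-point PLS effect in both doses, SD 21, 245 per arm, negligible drop-out), per-dose 6MWT power under the planned gatekeeping is at most about 71%, against the unlabelled 97% and 80%. At 30 m in both doses it is about 69–71% per dose and 79–81% for at least one dose, for any non-negative PLS/6MWT correlation.

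A reader might infer more, but the documents do not support it:

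- **That the 6MWT power was miscalculated, or that the trial is too small.** The stand-alone arithmetic is right, and sample size, alpha and test procedure are unaffected.
- **That the procedure can never reach 97% or 80%.** The ceiling follows from the 5-point assumption and rises with a larger true PLS effect.
- **That the ceiling is only about 65%, because Protocol 10.3.1 names just the other primary hypothesis for recycled alpha.** If the recycled test rejects that primary, both primaries are rejected, and the sentence in 10.3.1 covering that case can extend to the second dose's 6MWT. SAP 6.2.5 says so expressly.
- **That SAP section 2 is false where it says "The study is designed to have enough power for the primary and secondary hypotheses testing".** It gives no number, and at 30 m the chance of success on at least one dose is about 80%, in line with the trial's either-or criterion.

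**What to change.** In Protocol 10.4, label 97% and 80% as marginal (stand-alone, ungated) power at two-sided 0.025. Then add:

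> Under the gatekeeping procedure and the planning assumption of a 5-point PLS effect (SD 21) in both doses, the power to reject a given dose's 6MWT hypothesis is at most about 71%; at 30 m in both doses it is about 69–71% per dose and 79–81% for at least one dose, for any non-negative PLS/6MWT correlation.

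The cost is one label and one sentence.
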